11.5 Vital Signs

Vital signs (pulse and systolic and diastolic blood pressure) will be taken at the times indicated in [Table 1](#). Vital signs should be taken after the subject is seated for at least 5 minutes.

11.6 Best-Corrected Visual Acuity

To evaluate changes in BCVA over the study period, BCVA will be assessed using the ETDRS VA chart and performed for both eyes at the times indicated in [Table 1](#).

The BCVA test should be performed prior to pupil dilation, and distance refraction should be carried out before BCVA is measured. Initially, letters are read at a distance of 4 metres from the chart. If <20 letters are read at 4 metres, testing at 1 metre should be performed. BCVA is to be reported as number of letters read correctly by the subject.

For BCVA, assessors will be appropriately qualified for conducting the assessment.

If a subject is not able to perform an assessment due to poor VA, it will be documented accordingly in the eCRF and will not be recorded as a protocol deviation.

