13.2 Procedure for Accounting for Missing Data

All reasonable efforts will be made to obtain complete data for both eyes on all subjects. However, missing observations may occur. Management of dropout and missing observations will depend on their nature and frequency and will be discussed as part of the Data Review meeting before database lock.

Safety data will be analysed on observed data (missing data will not be imputed). The analysis of efficacy endpoints will be performed using the last observation carried forward approach for imputation of missing data.

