4.2 Conventions

Summary statistics will be presented for continuous variables, by way of number of subjects, mean, standard deviation (SD), median, first and third quartiles (Q1 and Q3, respectively), 5th and 95th percentiles (P05 and P95, respectively), minimum and maximum. For categorical variables including binary variables, counts and percentages will be presented. Percentages will be calculated using the total number of eyes in the respective column or the total number of eyes with an assessment, the total number of treated subjects, depending on the nature of the analysis.

In addition, 95% 2-sided confidence intervals (CIs) will be presented, where specified. The 95% CI of the mean value of an assessment will be calculated using the t-test formula. The 95% CI of the mean of change from baseline of an assessment will be calculated using the t-test formula. In case of percentages, the CI will be computed using the Clopper-Pearson method. (See [Section 4.21](#) for the corresponding SAS code).

No formal statistical comparison will be performed.

Summary statistics will be presented by period and overall for all endpoints. For selected endpoints (see details below), summary statistics will also be presented by Surgery Window (Short [<6 months], Medium [6-12 months] and Long [>12 months]) and overall. Where appropriate, summary statistics will be displayed by eye (SE1 and SE2), and by period.

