4.8 Handling of Missing Values

The number, pattern and timing of missing data will be examined along with the reasons for withdrawal or for missing data.

The safety analyses will be performed using the ‘observed case’ method. In the efficacy analysis, observed case method will be applied as main analysis for categorical and continuous endpoints. The following supportive analysis will be performed for BCVA related endpoints: both categorical endpoints and continuous endpoints will be imputed using the ‘Last Observation Carried Forward’ (LOCF) method with the last available measurement prior to missing (see details in [Section 4.16.1](#)).

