4.16.1 Visual Acuity

Best-corrected visual acuity (BCVA) and change from baseline will be summarised by visit, by eye, by period as well as overall. The corresponding 95% CIs will be calculated (See [Section 4.2](#)).

Furthermore, the proportion of eyes with a ≥ 10 letters increase, a ≥ 15 letters increase, and an increase or a loss < 5 letters (i.e. change from baseline > -5 letters) will be summarised by visit, by eye, by period as well as overall. The corresponding 95% CI will be presented (See [Section 4.2](#)).

The above main analyses will use the observed case method only. Imputation using LOCF method regardless of the reasons of missing data will be performed for supportive analyses (See [Section 4.8](#)).

In addition to the by-period, by-eye presentation mentioned above, as supportive analyses, for both continuous and categorical endpoints, the period 2 Study Eye 1 data will be presented by

remapping them to visits after their last visit in period 1 and calculating change from baseline using baseline at period 1 for the same eye (Study Eye 1). This way a full picture of Study Eye 1 treatment journey during the entire study will be presented.

For all assessments of periods 1 and 2 of Study Eye 1, the data records will be assigned to calculated visit window (using study day) as described in [Table 2](#) below. The window of the visits following baseline (including unscheduled visits) will be constructed in such a way that the upper limit of the interval falls half way between the two visits.

If a patient has more than one assessment included within a window, the assessment closest to the target day will be used. In case of ties between observations located on different sides of the target date, the value with the later date will be used.

Table 2 **Visit Assignment Windows**

Day / Month	Target Day	Day Range included in the visit
Baseline	0	The last assessment on or before day 0
Day 1	1	Day 1
Day 3	3	Day 2 to 5
Day 7	7	Day 6 to 10
Day 14	14	Day 11 to 22
Month 1	30	Day 23 to 61
Month 3	91	Day 62 to 136
Month 6	182	Day 137 to 272
Month 9	273	Day 228 to 318
Month 12	365	Day 319 to 410
Month 15	456	Day 411 to 501
Month 18	548	Day 502 to 593
Month 21	639	Day 594 to 684
Month 24	731	Day 685 onwards

Both continuous and categorical endpoints for BCVA will be summarised by subgroups mentioned in [Section 4.7](#).

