4.17 Safety Analysis

Safety analysis will be performed on the All Treated Subjects analysis set using observed cases only.

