4.20 Changes in Planned Analyses from the Protocol

There are some changes to the planned analyses described in the protocol.

1. The protocol refers to the assessment of Fixation Location. Because of a change in the way microperimetry data are collected, fixation location is not available in the database. Therefore, Fixation Location was removed from the SAP.
2. The protocol mentions that specific analyses of the sensitivity points (microperimetry) will be performed. These analyses are not included in the SAP as they are considered as exploratory across the BIIB111 program and will be performed as post-hoc analyses, if needed to be consistent with other studies in the same program.
3. For consistency of other studies in the program, time to resolution of AEs will not be summarized.
3. The protocol specifies that LOCF will be used as imputation method for efficacy analyses. The main analyses of categorical and continuous efficacy endpoints will use the observed case method, as the main purpose of the study is the evaluation of BCVA from a safety perspective. Additional supportive analyses of BCVA-related endpoints, including LOCF imputation, will be applied and are described in detail in [Section 4.16.1](#).

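### An eye recorded as unable to do the BCVA test because of poor vision has no stated score; if left blank, the letter-loss tables omit it and LOCF may count it as stable

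*Protocol*

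**What the plan says.** **Scoring.** Protocol 11.6 tests at 4 metres, moves to 1 metre if fewer than 20 letters are read, and states that "BCVA is to be reported as number of letters read correctly by the subject". It then adds: "If a subject is not able to perform an assessment due to poor VA, it will be documented accordingly in the eCRF", and says that this is not a protocol deviation. No letter value is attached. The sentence stands in the BCVA section, although its wording is general.

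**Missing data.** Protocol 13.2: "Safety data will be analysed on observed data (missing data will not be imputed". SAP 4.17: "Safety analysis will be performed on the All Treated Subjects analysis set using observed cases only". SAP 4.8 also makes observed cases the main method for the efficacy BCVA tables. The reason given in SAP 4.20 is "as the main purpose of the study is the evaluation of BCVA from a safety perspective".

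**LOCF.** SAP 4.8 takes the last available measurement before the missing one. SAP 4.16.1: "Imputation using LOCF method regardless of the reasons of missing data will be performed for supportive analyses".

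**Denominator.** SAP 4.2 leaves a choice: "Percentages will be calculated using the total number of eyes in the respective column or the total number of eyes with an assessment".

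**Tables affected.** SAP 4.17.1 (losses of at least 5, 10 and 15 letters), SAP 4.16.1 (mean change, gains, and the category of a gain or a loss under 5 letters), and SAP 4.17.11.4 (loss of at least 15 letters at Month 12 by immune status).

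**The concern.** Safety is the study's only objective. BCVA is the first safety measure listed, and protocol 5.4 names loss of visual acuity as an identified risk. If an eye becomes too poor to test and carries no number, it has no change from baseline and cannot appear as a loss. It would be missing because of the outcome being measured, and a method chosen for its safety perspective would omit the worst result. LOCF would not reliably correct this. It keeps a loss already recorded, but if the last score predates the loss it can place the eye in a favourable category.

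Low scores are foreseeable. SE2 may be treated below 34 letters with the eligibility committee's agreement (protocol 7.1). For subjects first treated in an antecedent study, the 34-letter entry criterion covers only the untreated eye (protocol 8.1).

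**Working it through.** The documents give no figure to reproduce: there is no formal sample size calculation and no expected number of untestable eyes. The direction follows from the rules; the size is illustrated under stated assumptions.

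**Step 1. Follow one eye through the rules (assumed scores).** Baseline 60 letters, Month 6 58 letters, Month 12 unable to perform and left blank.

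| Handling at Month 12 | Change | Category |
|---|---|---|
| Observed case | none | absent from every numerator |
| LOCF | 58 − 60 = −2 | gain or loss under 5 letters |
| Scored 0 | 0 − 60 = −60 | loss of at least 5, 10 and 15 letters |

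**Step 2. Mean change**, with 60 eyes and the other 59 assumed unchanged:
- Scored 0: −60/60 = −1.0 letter
- Observed case: 0/59 = 0.0
- LOCF: −2/60 = −0.03

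**Step 3. Proportion losing at least 15 letters.** Inputs: about 60 subjects, hence about 60 eyes per study-eye column, and about 20 subjects per surgery window (protocol 7.1, 13.1). The assumed 3 true losers in 60 is set near the 4/79 = 5.1% in protocol 5.4, for scale only. The number of unscored losers is assumed, over the range 0 to 3. Intervals are Clopper-Pearson, as in SAP 4.2: lower limit = the 0.025 quantile of Beta(x, n − x + 1), upper limit = the 0.975 quantile of Beta(x + 1, n − x).

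| Unscored losers | Assessed eyes as denominator | All eyes as denominator |
|---|---|---|
| 0 | 3/60 = 5.0% (1.0–13.9) | 3/60 = 5.0% (1.0–13.9) |
| 1 | 2/59 = 3.4% (0.4–11.7) | 2/60 = 3.3% (0.4–11.5) |
| 2 | 1/58 = 1.7% (0.0–9.2) | 1/60 = 1.7% (0.0–8.9) |
| 3 | 0/57 = 0.0% (upper 6.3) | 0/60 = 0.0% (upper 6.0) |

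The numerator falls under either denominator.

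**Step 4. Small groups, one true loser left unscored:**
- Surgery window of 20: 1/20 = 5.0% (0.1–24.9) becomes 0/19 (upper limit 17.6%) or 0/20 (16.8%).
- Assumed immune-status group of 10 eyes: 1/10 = 10.0% (0.3–44.5) becomes 0/9 (upper limit 33.6%) or 0/10 (30.8%).

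**Step 5. Does LOCF reach the loss categories?** This is not explicit. SAP 4.8 applies LOCF to BCVA-related endpoints, and SAP 4.17.1 puts the losses in the same tables as SAP 4.16.1, but SAP 4.17 limits safety to observed cases. The favourable category sits in SAP 4.16.1, so LOCF does reach that.

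**The case against.** **The sentence may not be about BCVA scoring.** The Version 3.0 summary of changes shows that it came from a general preamble to the efficacy assessments. Poor acuity may prevent microperimetry, for example, whereas in an acuity test it is the result. This stands as a caution. The current sentence is in the BCVA section all the same, and its wording does not exclude the BCVA test.

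**The category may be empty.** An eye that reads nothing at 1 metre has read 0 letters, which is an observed value. A reader might infer that every eye reading no letters is dropped; the documents do not support that. The bias arises only if an eye is recorded as unable to perform and its score is blank. The eCRF, which would settle this, is not available to us.

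**The event is captured elsewhere.** Vision loss is an SAE criterion (protocol 11.1.1.2), and Visual Acuity Reduced events are tabulated by eye, period and surgery window (SAP 4.17.10), so the plan cannot be said to hide these losses. The cover is partial: it rests on investigator reporting, and protocol 11.1.1.1 excludes worsening judged consistent with natural progression.

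**A later review could deal with it.** SAP 4.8 says "The number, pattern and timing of missing data will be examined along with the reasons for withdrawal or for missing data", and protocol 13.2 provides a data review before lock. Either may reveal such eyes, but neither states a score, and in an open-label study the score is better fixed beforehand.

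**A 0 has costs.** It could put transient zeros into the Day 1 and Day 3 tables, and as a baseline it would hide later decline. Both points stand, and the remedy has to address them.

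**Conclusion.** The gap is real but conditional. If an eye is recorded as unable to perform BCVA because of poor vision and its score is blank, the stated rules understate letter loss, and LOCF may class the eye as stable. That rests on reading the general sentence in protocol 11.6 as including the BCVA test, and on the blank field.

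The size is unknown and probably involves few eyes. A reader might infer that the study's safety conclusion would change. The documents do not support that: no formal test depends on these figures, and with one unscored eye in 60 the intervals largely overlap. The effect is clearest in small groups, where a single event can disappear. The bias is confined to the BCVA tables. Severity is minor to should-fix, with medium confidence.

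**What to change.** 1. In SAP 4.8, 4.16.1 and 4.17.1, and by reference in 4.17.11.4, state that a post-treatment BCVA not obtainable because of poor vision is analysed as 0 letters in both the observed-case and LOCF tables and stays in the denominator. Values missing for any other reason stay missing.
2. Report the number of eyes scored this way by visit, eye and period, so that early post-operative zeros (Day 1 and Day 3, for example) can be separated from later ones. Repeat the table without these eyes.
3. Flag any SE1 eye whose Period 2 baseline is an assigned 0 under the last-non-missing rule in SAP 4.3, since it cannot show further loss. Read it with the change from Period 1 baseline already planned in SAP 4.16.1. That analysis is not available for the 6 subjects first treated in an antecedent study.

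The cost is one scoring sentence, one count row, one repeat table and a flag, using a reason that protocol 11.6 already has documented. The downside is that 0 is a floor and not a measured value; the repeat table shows how much depends on it. If the eCRF already records 0 for these eyes, the scoring sentence only confirms existing practice.

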11.7 Microperimetry

Microperimetry will be conducted on both eyes at the times indicated in [Table 1](#).

Microperimetry will be conducted by certified technicians to assess changes in retinal sensitivity within the macula. All microperimetry images will be sent by the sites to a Central Reading Centre (CRC) for review. For complete technical specifications for microperimetry, refer to the Study Operations Manual (which will include procedures from the CRC regarding how measurements are to be taken).

11.8 Fundus Autofluorescence

To assess changes in the area of viable retinal tissue, fundus AF will be performed on both eyes at the times indicated in [Table 1](#).

All fundus AF images will be performed by certified technicians at the site after dilation of the subject's pupil and sent to a CRC for review; the CRC will enter the data into the electronic data capture (EDC) system. For complete technical specifications for AF, refer to the Study Operations Manual (which will include procedures from the CRC regarding how measurements are to be taken).

11.9 Spectral Domain Optical Coherence Tomography

SD-OCT will be performed on both eyes at the times indicated in [Table 1](#).

SD-OCT measurements will be taken by certified technicians at the site after dilation of the subject's pupil. All OCT scans will be submitted by the sites to a CRC where the scans will be evaluated; the CRC will enter the data into the EDC system. SD-OCT will be used to quantify integrity of the ellipsoid zone and reduction in the signal from the outer nuclear layer and choroid. In addition, foveal changes will be assessed. For complete technical specifications for SD-OCT, refer to the Study Operations Manual (which will include procedures from the CRC regarding how measurements are to be taken).

11.10 Full Ophthalmic Examination

A full ophthalmic examination will be performed for both eyes at the times indicated in [Table 1](#).

Each ophthalmic examination will include IOP, slit lamp examination, lens opacity grading, and dilated ophthalmoscopy. The same slit lamp machine and lighting conditions should be used across study visits for any given subject.

In addition to the parameters listed above, subjects will be carefully examined for the presence of intraocular inflammation after vector administration. Cataract can also develop as a result of the vitrectomy procedure and can potentially affect VA. Pre-operative grading of lens opacity and colour should therefore be documented by the established clinical LOCS III. A recent study has shown that cataract surgery is effective in subjects with CHM and without any specific risks ([Edwards, Jolly et al. 2016](#)). Subjects who develop cataracts may undergo cataract surgery if deemed clinically necessary. If cataract surgery is performed, it should be carried out at least 4 weeks before Month 12 (Visit 9) for the respective eye.

11.11 7-Field Colour Fundus Photography

Seven-field colour fundus photography will be performed for both eyes at the times indicated in [Table 1](#).

Fundus photography will be performed by certified technicians following pupil dilation. Stereo photos should be performed for fields 1, 2 and 3. All fundus photographs will be sent by the sites to the CRC for review; the CRC will enter the data into the EDC system. For complete technical specifications for fundus photography, refer to the Study Operations Manual.

12 ASSESSMENT OF EFFICACY

The following assessments are primary safety assessments that will also be considered secondary efficacy endpoints.

12.1 Best-Corrected Visual Acuity

See [Section 11.6](#).

12.2 Fundus Autofluorescence

See [Section 11.8](#).

12.3 Spectral Domain Optical Coherence Tomography

See [Section 11.9](#).

12.4 Microperimetry

See [Section 11.7](#).

13 STATISTICAL CONSIDERATIONS

13.1 Sample Size

Approximately 60 subjects are planned to be enrolled in the study. A total of 120 treated eyes is considered sufficient to characterise the immunological profile of bilateral AAV2-REP1 administration, which is the key concern of gene therapy re-administration.

13.2 Procedure for Accounting for Missing Data

All reasonable efforts will be made to obtain complete data for both eyes on all subjects. However, missing observations may occur. Management of dropout and missing observations will depend on their nature and frequency and will be discussed as part of the Data Review meeting before database lock.

Safety data will be analysed on observed data (missing data will not be imputed). The analysis of efficacy endpoints will be performed using the last observation carried forward approach for imputation of missing data.

13.3 Analysis Sets

The ‘All Treated Subjects’ Analysis Set will consist of all subjects who attend the ‘Day of Surgery’ visit of Period 1 (or, of Period 2, for subjects who received AAV2-REP1 treatment in SE1 in an antecedent study). The All Treated Subjects Analysis Set will be the primary population for demographics, baseline characteristics, and safety and efficacy analyses.

13.4 Descriptive Statistics and Conventions

Detailed specifications of the planned analyses will be included in a separate Statistical Analysis Plan (SAP).

Continuous variables (including changes from Baseline) will be summarised over time using descriptive statistics (i.e., mean, standard deviation, 95% confidence interval [CI], median, first and third quartiles, fifth and ninety-fifth percentiles, minimum, and maximum). Categorical variables (including shifts from Baseline) will be described over time using counts, percentages, and 95% CIs.

Baseline is defined, for each eye and each period, as the last non-missing value prior to treatment of the respective period, in the respective eye.

13.5 Demographics and Baseline Characteristics

Demographics will be summarised for all subjects combined. Age at the date of the Period 1 informed consent will be calculated. Baseline ocular characteristics will be summarised by eye and period.

13.6 Safety Analyses

No statistical tests will be performed.

13.6.1 Visual Acuity

See [Section 13.7.1](#).

13.6.2 Ophthalmic Examination

IOP and change from Baseline in IOP will be summarised by eye, period and visit. Abnormal slit lamp examination findings and dilated ophthalmoscopy findings will be summarised by eye, period and visit. Lens opacity categories and shifts from baseline will be summarised by eye, period and visit.

13.6.3 Spectral Domain Optical Coherence Tomography

See [Section 13.7.2](#).

13.6.4 Fundus Autofluorescence

See [Section 13.7.3](#).

13.6.5 7-Field Colour Fundus Photography

Categories of colour fundus photography findings will be summarised by eye, period and visit.

13.6.6 Microperimetry

See [Section 13.7.4](#).

13.6.7 Adverse Events

AEs will be coded using the Medical Dictionary for Regulatory Affairs, version 21.0 or higher. Events will be summarised by system organ class and preferred term and eye. The number of eyes with an AE, as well as the number of events, will be summarised, by period and eye. Similar summaries will be produced for study drug/procedure-related AEs, AEs leading to discontinuation, and SAEs. AEs will also be summarised by maximum severity, relationship to study drug/procedure, and time to onset and resolution.

13.6.8 Immunogenicity and Vector shedding

Vector shedding and immune response profiles will be described.

13.6.9 Vital Signs

Vital signs will be summarised by period and visit.

13.7 Efficacy Analyses

13.7.1 Visual Acuity

The proportion of subjects with a ≥ 10 - and ≥ 15 -letter improvement from baseline in BCVA will be summarised by eye, period and visit. Mean BCVA and mean change from Baseline in BCVA will be tabulated by eye, period and visit. The proportion of subjects with a ≥ 10 - and ≥ 15 -letter improvement from baseline in BCVA will be summarised by eye, period and visit. Mean BCVA and mean change from Baseline in BCVA will be tabulated by eye, period and visit.

